6.3.2 Disease Parameters

Measurable disease: Measurable lesions are defined as those that can be accurately measured in at least one dimension (longest diameter to be recorded) as:

- By chest x-ray: $\geq 20 \text{ mm}$
- By CT scan:
 - Scan slice thickness of 5 mm or under: as \ge 10 mm
 - O Scan slice thickness of >5 mm: double the slice thickness

Version Date: 09/24/2021

• With calipers on clinical exam: ≥10 mm

All tumor measurements must be recorded in millimeters (or decimal fractions of centimeters).

Note: Tumor lesions that are situated in a previously irradiated area might or might not be considered measurable.

Malignant lymph nodes. To be considered pathologically enlarged and measurable, a lymph node must be ≥ 15 mm in short axis when assessed by CT scan (CT scan slice thickness recommended to be no greater than 5 mm). At baseline and in follow-up, only the short axis will be measured and followed.

Non-measurable disease. All other lesions (or sites of disease), including small lesions (longest diameter <10 mm or pathological lymph nodes with ≥10 to <15 mm short axis), are considered non-measurable disease. Bone lesions, leptomeningeal disease, ascites, pleural/pericardial effusions, lymphangitis cutis/pulmonitis, inflammatory breast disease, and abdominal masses (not followed by CT or MRI), are considered as non-measurable.

Note: Cystic lesions that meet the criteria for radiographically defined simple cysts should not be considered as malignant lesions (neither measurable nor non-measurable) since they are, by definition, simple cysts.

'Cystic lesions' thought to represent cystic metastases can be considered as measurable lesions, if they meet the definition of measurability described above. However, if non-cystic lesions are present in the same patient, these are preferred for selection as target lesions.

Target lesions. All measurable lesions up to a maximum of 2 lesions per organ and 5 lesions in total, representative of all involved organs, should be identified as **target lesions** and recorded and measured at baseline. Target lesions should be selected on the basis of their size (lesions with the longest diameter), be representative of all involved organs, but in addition should be those that lend themselves to reproducible repeated measurements. It may be the case that, on occasion, the largest lesion does not lend itself to reproducible measurement in which circumstance the next largest lesion which can be measured reproducibly should be selected. A sum of the diameters (longest for non-nodal lesions, short axis for nodal lesions) for all target lesions will be calculated and reported as the baseline sum diameters. If lymph nodes are to be included in the sum, then only the short axis is added into the sum. The baseline sum diameters will be used as reference to further characterize any objective tumor regression in the measurable dimension of the disease.

Non-target lesions. All other lesions (or sites of disease) including any measurable lesions over and above the 5 target lesions should be identified as **non-target lesions** and should also be recorded at baseline. Measurements of these lesions are not required, but the presence, absence, or in rare cases unequivocal progression of each should be noted throughout follow-up.

6.3.3 Methods for Evaluation of Measurable Disease

All measurements should be taken and recorded in metric notation using a ruler or calipers. All baseline evaluations should be performed as closely as possible to the beginning of treatment and never more than 4 weeks before the beginning of the treatment.

The same method of assessment and the same technique should be used to characterize each identified and reported lesion at baseline and during follow-up. Imaging-based evaluation is preferred to evaluation by clinical examination unless the lesion(s) being followed cannot be

Version Date: 09/24/2021

imaged but are assessable by clinical exam.

Clinical lesions: Clinical lesions will only be considered measurable when they are superficial (e.g., skin nodules and palpable lymph nodes) and ≥10 mm diameter as assessed using calipers (e.g., skin nodules). In the case of skin lesions, documentation by color photography, including a ruler to estimate the size of the lesion, is recommended.

Chest x-ray: Lesions on chest x-ray are acceptable as measurable lesions when they are clearly defined and surrounded by aerated lung. However, CT is preferable.

Conventional CT and MRI: This guideline has defined measurability of lesions on CT scan based on the assumption that CT slice thickness is 5 mm or less. If CT scans have slice thickness greater than 5 mm, the minimum size for a measurable lesion should be twice the slice thickness. MRI is also acceptable in certain situations (e.g. for body scans).

Use of MRI remains a complex issue. MRI has excellent contrast, spatial, and temporal resolution; however, there are many image acquisition variables involved in MRI, which greatly impact image quality, lesion conspicuity, and measurement. Furthermore, the availability of MRI is variable globally. As with CT, if an MRI is performed, the technical specifications of the scanning sequences used should be optimized for the evaluation of the type and site of disease. Furthermore, as with CT, the modality used at follow-up should be the same as was used at baseline and the lesions should be measured/assessed on the same pulse sequence. It is beyond the scope of the RECIST guidelines to prescribe specific MRI pulse sequence parameters for all scanners, body parts, and diseases. Ideally, the same type of scanner should be used, and the image acquisition protocol should be followed as closely as possible to prior scans. Body scans should be performed with breath-hold scanning techniques, if possible.

PET-CT: At present, the low dose or attenuation correction CT portion of a combined PET-CT is not always of optimal diagnostic CT quality for use with RECIST measurements. However, if the site can document that the CT performed as part of a PET-CT is of identical diagnostic quality to a diagnostic CT (with IV and oral contrast), then the CT portion of the PET-CT can be used for RECIST measurements and can be used interchangeably with conventional CT in accurately measuring cancer lesions over time. Note, however, that the PET portion of the CT introduces additional data which may bias an investigator if it is not routinely or serially performed.

Ultrasound: Ultrasound is not useful in assessment of lesion size and should not be used as a method of measurement. Ultrasound examinations cannot be reproduced in their entirety for independent review at a later date and, because they are operator dependent, it cannot be guaranteed that the same technique and measurements will be taken from one assessment to the next. If new lesions are identified by ultrasound in the course of the study, confirmation by CT or MRI is advised. If there is concern about radiation exposure at CT, MRI may be used instead of CT in selected instances.

Endoscopy, Laparoscopy: The utilization of these techniques for objective tumor evaluation is not advised. However, such techniques may be useful to confirm complete pathological response when biopsies are obtained or to determine relapse in trials where recurrence following complete response (CR) or surgical resection is an endpoint.

Tumor markers: Tumor markers alone cannot be used to assess response. If markers are initially above the upper normal limit, they must normalize for a patient to be considered in complete

Version Date: 09/24/2021

clinical response. Specific guidelines for both CA-125 response (in recurrent ovarian cancer) and PSA response (in recurrent prostate cancer) have been published(88-90). In addition, the Gynecologic Cancer Intergroup has developed CA-125 progression criteria which are to be integrated with objective tumor assessment for use in first-line trials in ovarian cancer(91).

Cytology, Histology: These techniques can be used to differentiate between partial responses (PR) and complete responses (CR) in rare cases (e.g., residual lesions in tumor types, such as germ cell tumors, where known residual benign tumors can remain).

The cytological confirmation of the neoplastic origin of any effusion that appears or worsens during treatment when the measurable tumor has met criteria for response or stable disease is mandatory to differentiate between response or stable disease (an effusion may be a side effect of the treatment) and progressive disease.

FDG-PET: While FDG-PET response assessments need additional study, it is sometimes reasonable to incorporate the use of FDG-PET scanning to complement CT scanning in assessment of progression (particularly possible 'new' disease). New lesions on the basis of FDG-PET imaging can be identified according to the following algorithm:

- Negative FDG-PET at baseline, with a positive FDG-PET at follow-up is a sign of PD based on a new lesion.
- No FDG-PET at baseline and a positive FDG-PET at follow-up: If the positive FDG-PET at follow-up corresponds to a new site of disease confirmed by CT, this is PD. If the positive FDG-PET at follow-up is not confirmed as a new site of disease on CT, additional follow-up CT scans are needed to determine if there is truly progression occurring at that site (if so, the date of PD will be the date of the initial abnormal FDG-PET scan). If the positive FDG-PET at follow-up corresponds to a pre-existing site of disease on CT that is not progressing on the basis of the anatomic images, this is not PD.
- FDG-PET may be used to upgrade a response to a CR in a manner similar to a biopsy in cases where a residual radiographic abnormality is thought to represent fibrosis or scarring. The use of FDG-PET in this circumstance should be prospectively described in the protocol and supported by disease-specific medical literature for the indication. However, it must be acknowledged that both approaches may lead to false positive CR due to limitations of FDG-PET and biopsy resolution/sensitivity.

Note: A 'positive' FDG-PET scan lesion means one which is FDG avid with an uptake greater than twice that of the surrounding tissue on the attenuation corrected image.

6.3.4 Response Criteria

In addition to the standard RECIST response criteria below, the following will be also applicable to evaluation of response for skin lesions for this study:

Target Lesions:

- Complete Response (CR): Disappearance of skin lesions per mSWAT/Global Response Score and/or any circulating leukemic cells must also be documented, if initially present.
- Partial Response (PR): At least a 50% decrease in ATL skin lesions (per mSWAT/Global Response Score) and/or in the absolute number of circulating leukemic cells, if initially present.

Non-Target Lesions:

Version Date: 09/24/2021

• Complete Response (CR): Disappearance of skin lesions per mSWAT/Global Response Score and/or any circulating leukemic cells must also be documented, if initially present.

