1.2.2.4 LYMB Experience with Alemtuzumab Treatment for ATL

Examination of leukemic cells in fine needle aspiration biopsies demonstrated that CD52 is highly expressed in over 90% of ATL cells and is comparable to the level of CD25 expression observed on the tumor cells in these patients(33). In preclinical studies alemtuzumab prolonged the survival of mice with human MET-1 ATL comparable to that of tumor-free controls(14). These results were the basis of a single institution, nonrandomized, open-label Phase II clinical trial which was initiated to assess the antitumor activity and toxicity profile of alemtuzumab in patients with HTLV-1 associated ATL, excluding those with the smoldering subtype(33). Twenty-nine patients with chronic, acute and lymphomatous HTLV-1 associated ATL were treated with intravenous alemtuzumab 30 mg three times weekly for a maximum of 12 weeks in this single institution, non-randomized, open-label Phase II trial. All patients were evaluable for AEs and response with the exception that one patient was not evaluable for response because of early withdrawal. The overall response rate was 15 out of 29 patients (95% CI: 32.5 to 70.6%), but response rate varied widely within the different ATL subtypes. Only 1 of 9 patients with lymphomatous subtype responded, in contrast to the acute subtypes (12 of 17) and 2 of 3 patients with severe chronic ATL. The most common adverse events were infusion reactions that were grade 1 or 2 (CTCAE v2.0) occurring mainly in the first week of alemtuzumab administration and the median time to recovery of ALC to ≥ 200 cells/ μ L was 1.8 months. All patients developed CMV antigenemia, but only 3 of the patients became symptomatic and required therapeutic antiviral treatment. In the 15 responding patients, the median time to response was 1.1 month (range 1.0 to 4.2 months), but the median response duration (3.4 months) and the median progression free survival (2.0 months) were short producing a short period of clinical benefit, median time to treatment failure (1.6 months) and median survival (5.9 months) with only 6 patients (21%) alive at the date of the data cutoff (November 2009) (Figure 3).

Survival

[figure not shown]

Figure 3: Meier-Kaplan Plot of Survival of patients with ATL (3 chronic, 17 acute and 9 lymphomatous) who were treated with alemtuzumab

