1.2.3.4 Alemtuzumab in relapsed/refractory CTCL

The first reported prospective trial of alemtuzumab in CTCL was performed in Europe with 30 mg given intravenously for 12 weeks to 22 patients, 7 of whom with circulating Sézary cells(31). CD52 expression was confirmed by flow cytometry. ORR was 55% (7 CRs, 5 PRs), with median duration of response 12 months (range 5-32+).

Subsequent trials showed alemtuzumab was more effective in patients with circulating Sézary cells (B1-2) or erythrodermia (T4)(47). In a prospective trial, alemtuzumab 30 mg was given intravenously three times weekly for 4 weeks, then subcutaneously for 8 weeks to 19 patients with stage III-IV, T4 disease (one of whom had visceral metastases)(49). ORR was 84% (9 CRs, 7 PRs), median OS 41 months, PFS 6 months. There was minimal residual disease present in 11/16 patients with response.

In another prospective study, alemtuzumab 10 mg was given subcutaneously three times weekly for 6+ weeks to 18 patients with "leukemic" CTCL and two with MF (without circulating cells)(50). For L-CTCL ORR was 100% (16 CRs, 2 PRs) in blood, and 89% (8 CRs, 8 PRs) in skin. There were no responses in either of the two patients with MF.

1.2.3.5 Treatment of relapsed/refractory T-cell prolymphocytic leukemia (T-PLL) Similar to ATL, T-PLL is an aggressive mature T-cell malignancy which lacks approved first or second-line treatments(51). In a phase I trial of the purine nucleoside analogue nelarabine, the ORR was 20% for nelarabine alone, and 63% (13% CR) when combined with fludarabine(52). Retrospective data from 9 European centers showed ORR 76% with 60% CR and 16% PR when Alemtuzumab was given to 38 patients intravenously until maximal response or intolerance for median 5 weeks (range 2-82 days)(26). Median disease-free interval was 7 months (4-45 months). Of 12 patients retreated with Alemtuzumab following relapse, 42% achieved a second CR, and one a PR, with responses lasting 5-6 months. Median overall survival was 10 months overall, 16 months in patients who achieved CR, 9 months in those achieving PR, and 4 months in non-responders.

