6.3 RESPONSE CRITERIA

Response and progression will be evaluated in this study using the new international criteria proposed by the revised Response Evaluation Criteria in Solid Tumors (RECIST) guideline (version 1.1)(87). Changes in the largest diameter (unidimensional measurement) of the tumor lesions and the shortest diameter in the case of malignant lymph nodes are used in the RECIST criteria. Separately, patients with cutaneous involvement will have their skin disease evaluated by a dermatologist using the mSWAT tool [Appendix I]. Leukemic cells (Sezary or T-PLL) as percentage of PBMCs will also be assessed and reported separately.

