6.3.1 Definitions

Evaluable for toxicity: All patients will be evaluable for toxicity from the time of their first treatment with IL-15.

Evaluable for objective response: Only those patients who have measurable disease present at baseline, have completed the 6 weeks of therapy, and have had their disease re-evaluated will be considered evaluable for response. These patients will have their response classified according to the definitions stated below.

Evaluable Non-Target Disease Response: Patients who have lesions present at baseline that are evaluable but do not meet the definitions of measurable disease, have completed the 6 weeks of therapy, and have had their disease re-evaluated will be considered evaluable for non-target disease. The response assessment is based on the presence, absence, or unequivocal progression of the lesions.

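### The partial-response add-on in 6.3.4 joins skin and blood with and/or, so a fall in circulating cells alone can meet PR while skin is unchanged, and no rule combines nodes, skin and blood

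*Combined protocol and SAP*

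**What the plan says.** Section 6.3.4 places skin and blood criteria on top of RECIST 1.1: "In addition to the standard RECIST response criteria below, the following will be also applicable". Under target lesions, PR is "At least a 50% decrease in ATL skin lesions (per mSWAT/Global Response Score) and/or in the absolute number of circulating leukemic cells", qualified by whether the feature was present at the start. CR, under both target and non-target lesions, is worded differently: "Disappearance of skin lesions per mSWAT/Global Response Score and/or any circulating leukemic cells must also be documented, if initially present".

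The opening of 6.3 gives the same two compartments another role. For skin: "Separately, patients with cutaneous involvement will have their skin disease evaluated by a dermatologist using the mSWAT tool". For blood: "Leukemic cells (Sezary or T-PLL) as percentage of PBMCs will also be assessed and reported separately".

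Overall response is assigned in 6.3.4.3 from two tables. The table for measurable disease has columns for target, non-target and new lesions. The table for non-measurable disease has columns for non-target and new lesions, and no PR row. Neither mentions skin score or circulating cells.

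Eligibility (2.1.1.2) covers ATL, PTCL, T-PLL and stage III or IV CTCL with blood involvement and/or erythrodermia. Response rate is a secondary objective (1.1.2).

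**The concern.** Many patients eligible for this trial can have disease in nodes, skin and blood at once, so the response rate depends on how the compartments are combined. The PR line lets either skin or blood suffice. Unlike the CR line, it does not say that the finding must be documented as well as something else. The add-on also sets no progression threshold for skin or blood.

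Two assessors could therefore follow the text and classify the same patient differently, and the literal reading of the PR line favours response. Alemtuzumab depletes circulating lymphocytes, and the one data set in the document that shows both compartments has blood responding more often than skin. Any error would therefore tend to be upward. Section 10 enlarges the group at the MTD or maximum administered dose to 9 patients to describe clinical activity, and each reclassified patient moves that rate by 1/9 = 11 points.

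**Working it through.** **1. One patient under each part of the text.** Take a patient with skin and blood disease at baseline. At week 6 the circulating leukemic count has halved, skin is unchanged and there are no new lesions.

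- PR line in 6.3.4: met, through blood alone.
- Opening of 6.3: skin and blood are evaluated or reported separately, so neither clearly enters overall response. Blood is a percentage of PBMCs here but an absolute number in 6.3.4. The two can move differently when the other mononuclear cells also change, which both study drugs are expected to cause.
- Tables in 6.3.4.3: if the skin lesions are target lesions (calipers, at least 10 mm, 6.3.3), the target result is SD and so is the overall result. If the skin disease is diffuse and there is no measurable lesion, the result is Non-CR/non-PD, because that table has no PR row.

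The same findings can thus be PR, SD, Non-CR/non-PD, or outside overall response, and no sentence says which applies.

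**2. CTCL skin.** The 50% PR threshold is attached to ATL skin lesions only. The lead-in to 6.3.4 speaks of skin lesions for the study as a whole, so the restriction looks unintended, but it is what the line says.

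**3. Size, as an illustration.** The only figures that set the two compartments side by side are in 1.2.3.4, for n = 18: "For L-CTCL ORR was 100% (16 CRs, 2 PRs) in blood, and 89% (8 CRs, 8 PRs) in skin".

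- Blood responders: B = 16 + 2 = 18; 18/18 = 100%, as stated.
- Skin responders: S = 8 + 8 = 16; 16/18 = 88.9%, as stated (89%).

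Patient-level joint results are not given, so I use bounds from the margins.

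- Either compartment: at least max(B, S) = 18 and at most min(n, B + S) = 18, giving 18/18 = 100%.
- Both compartments: at least max(0, B + S − n) = 16 and at most min(B, S) = 16, giving 16/18 = 88.9%. Requiring nodal response or absence of progression as well can only lower this, so it is a ceiling.
- Difference: 2/18 = 11.1 points, or at least that. For 9 patients, 9 × 2/18 = 1 patient.

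**4. What does not move.** DLT and MTD (3.1.1, 3.1.2) use toxicity only. The sample size in Section 10 follows from 3+3 cohorts plus expansion. No test or power calculation rests on response.

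**The case against.** The strongest reply is that RECIST still governs. Objective response is restricted in 6.3.1: "Only those patients who have measurable disease present at baseline, have completed the 6 weeks of therapy". Overall response comes from tables in which no row turns a blood response into PR, and progression or a new lesion gives PD whatever the blood shows. Compartments are to be evaluated or reported separately, so a blood-only effect would be visible. Response is a secondary endpoint in an uncontrolled phase I trial.

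Most of this stands as a limit on the effect. It is why the wording can inflate the rate, and why a reader who infers that blood-only responses will be counted as overall responses goes beyond the text. It does not remove the ambiguity. The add-on says it applies as well as RECIST, and the tables are silent on it. A patient with erythrodermia and circulating cells may have no lesion RECIST can measure, and the add-on is then the only PR wording available.

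A reader might also infer that clearance of blood alone counts as CR, and might quote the CR margins: 16 of 18 in blood (89%) against 8 of 18 in skin (44%). The documents do not support that as the rule. CR requires disappearance, and the sentence demands that it also be documented for features present initially. This reads most naturally as an added condition covering patients with skin disease, blood disease or both. The and/or there needs clarifying, but the CR contrast depends on a strained reading and should not be used to size the problem.

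**Conclusion.** The point holds in this form. The PR add-on can be met by a 50% fall in circulating cells alone while skin disease present at baseline is unchanged, and Section 6.3 contains no rule for combining nodes, skin and blood. The blood metric differs between 6.3 and 6.3.4, and the PR line omits CTCL skin. For CR the issue is only unclear wording.

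The effect is on the interpretability of a secondary endpoint, with upward bias possible. The supportable illustration is 100% against at most 89%, about 1 patient in 9. It assumes that all 18 cited patients were assessed in both compartments and that the cited study's response thresholds resemble these. Carrying it to the expansion group further assumes that all 9 have skin and blood involved and respond at the same rates. The cited study used a lower, subcutaneous alemtuzumab schedule, and this trial also enrols ATL, PTCL and T-PLL, so the true size cannot be derived from the documents. The change should be made, but the primary objective does not depend on it.

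**What to change.** Amend Section 6.3 as follows.

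- **PR:** at least a 50% decrease in each of skin (mSWAT) and circulating leukemic cells where involved at baseline, plus at least RECIST PR where measurable disease exists, with no progression in any compartment.
- **CR:** clearance of every compartment involved at baseline, replacing and/or in that sentence.
- **Tables in 6.3.4.3:** add skin and blood entries so that overall response can be read off for any combination, including patients without measurable lesions. State what counts as progression in skin and blood, since the PR rule needs it.
- **Blood metric:** choose either the absolute number or the percentage of PBMCs and use it in both 6.3 and 6.3.4.
- **Scope:** delete ATL before skin lesions in the PR line.
- **Reporting:** keep the separate skin and blood results already planned in 6.3.

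This is a change of wording. Imaging, mSWAT and blood flow cytometry are already scheduled (3.4, 3.5, 5.1.1). One practical limit is that 5.1.1 allows the Clinical Center flow panel to be omitted or replaced by a standard one, so the text should say how blood response is classified when that happens. The cost is that the reported response rate may be lower.
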